There are not enough studies in the literature to clinically evaluate the changes in occlusal contact points according to different head positions using digital methods. This study aims to quantitatively evaluate the changes in occlusal contact points with digital interocclusal and facebow recordings taken in three different head positions. The hypothesis of the study is that there is no statistically significant difference in interocclusal contact points in different head postures.

Research will be supported by the Scientific Research Projects Coordination Unit of the University of Hacettepe, and an agreement will be reached with the Faculty of Dental Medicine of the Hacetepe University (Hacettepe University Dental Faculty [name]), the research center, in order to reach a positive conclusion about the necessary board decisions. Support address: University of Hacettepe [name].

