#### **Materials And Methods:**

The study will include healthy volunteers with natural dentition and no missing teeth. The study is planned to obtain a total of three different interocclusal records for three different head positions according to the appropriate head-neck-spine posture with an intraoral scanner, followed by digital facial arch recording and quantitative evaluation of changes in interocclusal contacts. No patient randomization was planned in the study, and direct digital interocclusal records and oJMA records were planned to be collected from each participant who met the inclusion criteria. Each volunteer who meets the inclusion criteria will be expected to carefully read the "Informed Consent Form" and then make his/her own decision about whether or not to participate in the study without any pressure. In line with the consent of the volunteer, surface scanning and digital dental arch records will be taken.

The intraoral scanner to be used in the study (TRIOS4; 3Shape A/S; Kopenhagen, Denmark) will perform surface scans of the mandibular arches and interocclusal records. TRIOS4 was chosen because all data to be acquired can be obtained without being subjected to laboratory stages that are prone to deformation, it offers a more comfortable and shorter procedure time for volunteers, it is manufactured following the latest technological developments, and it is a reliable and fast device with the support of literature knowledge. The device is manufactured in Denmark (3Sahep Trios A/S [name], [contact], [contact]) and its authorized representative in our country is BatiGroup Dental (BatiGroup Dental Dental Products Trade Anonim Şirketi, [name], [name], [contact]). The device is in pen form and the tip used in the mouth will be sterilized for each volunteer. Possible risks include a feeling of nausea that may occur during surface scanning in individuals with severe nausea reflex, but this can be seen during all dental procedures for individuals with nausea reflex and does not present a different risk.

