
# **Digital Interocclusal Record Groups**

Group 1 (G1): Digital interocclusal recording taken in the neutral position with the head aligned in the head-neck-spine plane

Group 2 (G2): Digital interocclusal recording taken in the position where the head is positioned at 30° flexion relative to the head-neck-spine plane

Group 3 (G3): Digital interocclusal recording with the head positioned in 45° extension relative to the head-neck-spine plane

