# Sample size and strength analysis

This study uses the PS Version 3.0 package. =0,50,  $\alpha$ =0,05, test strength 1-=080, repetition correlation r=0,20 is the default, and the total sample size is determined to be at least 36. But because working with a larger sample reduces the level of misunderstanding, it is desirable to work with as many patients as possible.

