#### **Randomization:**

The study was planned as a clinical trial. The planned digital interocclusional recordings for three different head positions will be completed in a single session, and the recording groups will not change. The total of three different records to be taken will not be subject to randomization in itself.

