#### **Statistical Evaluation**

Data from all volunteers participating in the study will be included in the statistical analysis. First, the Kolmogorov Smirnov adaptation test and the Shapiro-Wilk test are considered to be used to see if the data has a normal distribution. Subsequently, the differences between groups will be assessed using parametric or non-parametric statistical methods, depending on the case. Previous studies will be studied in detail, and comparisons will be evaluated using appropriate tests. Taking into account previous studies, it is envisaged that independent and dependent group tests, Kruskal Wallis, or one-way variance analysis, will be used.

Any possible change in the clinical research plan or process will be promptly notified to the research center, relevant institutions, boards, and healthy volunteers. Derogations from the clinical research plan are monitored and managed by the research center, and inconsistencies with the plan are expressly prohibited.

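### All three head positions come from the same volunteers, but the plan commits to no within-participant test, and the three-group tests it names are ordinarily for independent groups

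*Combined protocol and SAP*

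**What the plan says.** The design is within-participant throughout the combined protocol and SAP.

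- Materials and Methods plans to "obtain a total of three different interocclusal records for three different head positions", and states that "direct digital interocclusal records and oJMA records were planned to be collected from each participant who met the inclusion criteria".
- Digital Interocclusal Record Groups defines its groups as head positions, not as sets of people. G1, for example, is "Digital interocclusal recording taken in the neutral position with the head aligned in the head-neck-spine plane".
- Randomization adds: "The planned digital interocclusional recordings for three different head positions will be completed in a single session".
- Sample size and strength analysis allows for dependence between repeats: "repetition correlation r=0,20 is the default".

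Statistical Evaluation is less definite. After normality testing, "the differences between groups will be assessed using parametric or non-parametric statistical methods, depending on the case". It then says that, in the light of previous studies, "it is envisaged that independent and dependent group tests, Kruskal Wallis, or one-way variance analysis, will be used". It assigns none of these tests to the primary endpoint. Repeated-measures ANOVA, Friedman and mixed models are not named.

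The hypothesis, under Importance of the study, is that "there is no statistically significant difference in interocclusal contact points in different head postures".

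**The concern.** The documents describe one cohort, no comparator device and no between-person comparison. Independent-group tests therefore have no evident role in the primary question, yet they are listed beside dependent-group tests. The only three-group procedures named are Kruskal-Wallis, which treats all observations as coming from different people, and a one-way variance analysis, which in its ordinary form does the same.

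A test for independent groups leaves stable differences between people in its error term. When repeats are positively correlated, as the plan assumes, the error term is too large and the test rejects too seldom. Because the hypothesis is stated as an absence of difference, too few rejections favour it. The study is also unblinded and the choice of test is left open, so the conclusion could depend on which listed test is picked once the data are in hand.

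**Working it through.** **Inputs from the plan:** n = 36 participants, k = 3 positions, α = 0.05, r = 0.20.

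**Assumptions not in the plan:** normal data, equal variances and equal correlations (compound symmetry), mean patterns of 0/0.25/0.5 SD and 0/0/0.5 SD, and r = 0.5 as a sensitivity value.

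**The plan's own figure.** The sample size of 36 cannot be rebuilt uniquely, because the text available does not show which quantity the value 0.50 belongs to. At 80% power:

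- a paired t-test with 0.50 as the difference divided by the SD of differences gives 34;
- a paired t-test with 0.50 as the difference divided by the outcome SD, and r = 0.20, gives 53;
- repeated-measures ANOVA with f = 0.25 gives 43 participants;
- repeated-measures ANOVA with f = 0.50 gives 12 participants, or 36 records.

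The point below does not depend on which was meant.

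**Step 1: type I error by hand.** Take the outcome variance as 1. Under the null, the mean square between positions has expectation 1 − r. The error mean square of an ordinary one-way ANOVA has expectation 1, with 3 × 35 = 105 degrees of freedom. The F ratio is therefore centred near 1 − r instead of 1.

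- The critical value of F(2, 105) at 5% is 3.083.
- At r = 0.20: P[F(2, 105) > 3.083/0.8 = 3.854] = 2.4%.
- At r = 0.5: P[F(2, 105) > 3.083/0.5 = 6.166] = 0.3%.

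**Step 2: power of repeated-measures ANOVA by formula.** The noncentrality is λ = n Σ(μⱼ − μ̄)² / (1 − r), with 2 and 70 degrees of freedom.

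- Means 0/0.25/0.5: Σ = 0.0625 + 0 + 0.0625 = 0.125; λ = 36 × 0.125/0.8 = 5.625; power 53.6%.
- Means 0/0/0.5: Σ = 2 × (1/6)² + (1/3)² = 0.1667; λ = 36 × 0.1667/0.8 = 7.5; power 66.8%.

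**Step 3: simulation.** All four tests were applied to the same simulated data, with 40,000 trials per setting. The table gives the percentage significant at 0.05.

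| r | Means (SD) | One-way ANOVA | Repeated-measures ANOVA | Kruskal-Wallis | Friedman |
|---|---|---|---|---|---|
| 0.20 (plan) | 0/0/0 | 2.5 | 5.0 | 2.5 | 5.3 |
| 0.20 (plan) | 0/0.25/0.5 | 42 | 53 | 40 | 42 |
| 0.20 (plan) | 0/0/0.5 | 56 | 67 | 53 | 53 |
| 0.5 (assumed) | 0/0/0 | 0.3 | 4.9 | 0.3 | 5.1 |
| 0.5 (assumed) | 0/0.25/0.5 | 37 | 75 | 34 | 61 |

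Repeat runs moved these values by no more than about one percentage point, and they agree with Steps 1 and 2.

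**Step 4: disagreement on the same data** (r = 0.20, means 0/0.25/0.5). Repeated-measures ANOVA is significant and one-way ANOVA is not in about 11% of trials; the reverse occurs in 0.1%. Friedman and Kruskal-Wallis fall on opposite sides of 0.05 in about 18% of trials, split nearly evenly (about 10% and 8%).

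**Step 5: robustness at r = 0.20.** Null rejection by the two independent-group tests stays at about 2.4% to 2.6% with lognormal data, and is about 2.9% when the three correlations are 0.4, 0.2 and 0.

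**The case against.** The strongest reply is that the plan chooses no wrong test. It mentions dependent-group tests, promises appropriate ones, and is provisional in tone. Its sample-size paragraph shows that the planners knew the data were repeated. In a translated text, one-way variance analysis could mean the repeated-measures form. All of this is fair, and it makes the defect one of an open choice, not of a planned misuse. It does not close the gap: permitting a valid test is not selecting one, and Kruskal-Wallis has no repeated-measures reading.

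Other limits also stand.

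- The harm needs both an independent-group test and a positive within-person correlation. At r = −0.20 the ordinary tests would reject about 8% of the time under the null. Positive correlation is, however, the plan's own assumption.
- At r = 0.20 the rank branch loses almost no power. Its 18% disagreement partly reflects that Friedman and Kruskal-Wallis use the data differently. It supports fixing the test in advance; it does not show a power cost.
- The large losses rest on r = 0.5, which is not in the plan.
- The hypothesis is a conventional null. The plan does not say that non-significance will be read as proof of no difference.

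A further reply is that differences from the neutral position may be what is analysed. Testing each such difference against zero would indeed be within-participant. But G2 − G1 and G3 − G1 come from the same people and share G1, so comparing them with each other still requires a paired method.

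**Conclusion.** The concern holds and should be fixed. A fully within-participant design has no within-participant test committed to its primary comparison, and the three-group tests named are unsuitable for it in their ordinary form.

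At the plan's n = 36 and r = 0.20, using them would roughly halve the type I error, to about 2.5%. It would cost about 11 points of power on the ANOVA branch and almost none on the rank branch. The loss grows with the correlation: at an assumed r = 0.5 and means of 0/0.25/0.5 SD it is about 38 points for ANOVA (37% against 75%) and 26 to 27 points for ranks. False positives are not inflated when the correlation is positive.

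The power figures rest on normality, compound symmetry and the assumed mean patterns. The direction of the error rests only on positive within-person correlation.

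**What to change.** In Statistical Evaluation, state that G1, G2 and G3 are compared within participant by repeated-measures ANOVA or by a mixed model with a participant random effect, that the Friedman test is the rank alternative, and that pairwise contrasts are paired. For this comparison, delete independent-group tests, Kruskal-Wallis and ordinary one-way ANOVA. If the variance analysis was always meant as the repeated-measures form, say so.

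Two additions are useful in the same sentence: a sphericity correction for the repeated-measures ANOVA, and a multiplicity adjustment for the pairwise contrasts.

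The cost is one sentence of text, with no extra data or participants. It should be settled before the contact data are analysed.
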